The Chinese government reported the first cases of pneumonia of unknown origin on December 31, 2019,³ followed by a rapid increase in the Hubei province in China during the first weeks of January 2020, expanding in continental China and neighboring countries. The World Health Organization declared COVID-19 a public health emergency of international concern on January 30, 2020⁴ and a pandemic on March 11, 2020.⁵ The pandemic reached Latin America later than other continents, and the first case of COVID-19 in the region was reported in Brazil on February 26,⁶ followed by a case in Mexico on February 28, 2020 and subsequently spreading throughout the region during March 2020.

Policy responses to COVID-19 in Latin America have sought to reduce viral spread, increase the capacity of the health system response, mitigate negative consequences, and strengthen governance.⁷ Effectiveness studies of social distancing policies in China,^{8,9} India,¹⁰ European countries^{11,12}, the United States¹³ and worldwide¹⁴ have shown that these appear to be effective to reduce viral transmission.

Despite the heavy burden of the COVID-19 in Latin American countries, there have been few studies examining the effectiveness of COVID-19 policies.¹⁵⁻¹⁷ Likewise, few studies have explored variation at the local level in the effectiveness of COVID-19 policies.^{10,13,16} Inequalities in policy effectiveness can arise due to within-country differences at the local level due to their

geographical, sociodemographic, mobility patterns, and governance differences. In Latin America, high levels of poverty, urban density, household crowding, lack of safety nets, unemployment and precarious work cluster geographically and coexist with structural inequities in governance and built environments, thus creating barriers for effective compliance with preventive recommendations and for the implementation of well-functioning contact tracing and isolation mechanisms. Understanding the effectiveness of policies at the local level and exploring potential explanations for effect heterogeneity is essential to reduce the burden of the ongoing COVID-19 pandemic and inform the preparedness for future pandemics.

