In this study, we aim, first, to estimate the effectiveness of nonpharmaceutical interventions on SARS-COV2 transmission and COVID-19 mortality in Latin America; second, to examine the effect heterogeneity of transmission and mortality at the local level. Third, assuming we find evidence of moderate to substantial heterogeneity at the local level, we aim to explore potential explanations for this heterogeneity. We will use an interrupted time series method to estimate their effects in each local government, and random effects meta-analysis and meta-regression to obtain pooled effects, heterogeneity estimates and potential explanations.

Methods

Design and setting

The study is a natural experiment where we exploit the variation in the temporal and spatial implementation of policy interventions, aimed to reduce the spread and mortality of COVID-19 in Latin America. The unit of analysis are local governments, i.e. third-tier administrative levels such as municipalities, districts or cantons.

We will include all countries fulfilling the following eligibility criteria: (1) Spanish or Portuguese speaking countries in Latin America, and (2) availability of open data at the subnational level for either of the outcomes. Appendix I presents the eligible countries, the exclusion criteria and the sources of data for each excluded country. To date, eligible countries are Argentina, Brazil, Chile, Colombia, Costa Rica, Guatemala, Mexico, Paraguay, and Peru. These countries represent 80.9%

of the population in Latin America, and the vast majority of SARS-CoV-2 cases and COVID-19 deaths.

Interventions

We will examine the impact of several interventions to tackle the COVID-19 pandemic. These interventions include (i) policies aimed at reducing viral transmission, (ii) policies aimed at increasing the capacity of the health system's response, and (iii) policies aimed at mitigating the negative consequences of the epidemic and potential adverse effects of interventions. We will use the PoliMap taxonomy to categorise the examined policies.¹⁸ Table 1 describes the policy interventions in each policy domain included in the study.

Table 1. Policy interventions included in the study

Domain	Policy interventions

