The first model at the local level does not include covariates (see below). The second model (i.e. the meta-analysis), we will examine the change in heterogeneity after adjusting for several covariates at the local level. Local level covariates include projected population size in 2020, demographic density, age-structure of the population, household density and socioeconomic status. We will use data from official sources of information, primarily the latest national population census in each included country.

Statistical analysis

The Statistical Analysis Plan provides details on the modelling assumptions. We will use an interrupted time series design, where each local government acts as its own control.^{20,21} The main

strength of this design is its capacity to distinguish the effect of the intervention from secular change.²² We will use a Poisson regression to model the count data (for both outcomes) and accounting for overdispersion and secular trends.²³ A full discussion on potential biases and violations of assumptions can be found in the Statistical Analysis Plan.

In a second stage, we will use random effects meta analysis to pool the effect estimates for each intervention or combination of interventions. This analysis informs whether any implemented intervention was effective to reduce COVID-19 cases and deaths and the degree of heterogeneity between the effects at the local level. If we observe high levels of heterogeneity (defined as higher than 50%), we will also use standard meta-regression techniques to assess whether local level determinants (see *Covariates*) can explain the observed heterogeneity.

We will build the models and test the analytical strategy using publicly available data on COVID-19 cases and deaths from Finland and Sweden from January 1 to March 31.

References

2. United Nations Department of Economic and Social Affairs. World Social Report 2020: Inequality in a rapidly changing world. New York, United States: United Nations; 2020.
3. World Health Organization. Report of the WHO-China Joint Mission on Coronavirus Disease 2019 (COVID-19)2020. <https://www.who.int/docs/default-source/coronaviruse/who-china-joint-mission-on-covid-19-final-report.pdf> (accessed March 26, 2020).

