## Introduction

The COVID-19 pandemic is evolving quickly globally. By January 22, 2021, there were more than 112 million reported cases and more than 2.6 million deaths worldwide. Latin America is one of the worst-hit regions and accounts for 20.3% of the SARS-COV2 cases and 30% of the global deaths, despite having only 8% of the global population. The effectiveness of policies to reduce the spread of COVID-19 has been analyzed in several empirical studies. Nevertheless, few of these studies have included countries in Latin America or examined the effect heterogeneity and potential explanations for it. In this study we aim, first, to estimate the effectiveness of nonpharmaceutical interventions on SARS-COV2 transmission and COVID-19 mortality in Latin America; second, to examine the effect heterogeneity of transmission and mortality at the local level. Third, assuming we find evidence of moderate to substantial heterogeneity at the local level, we aim to explore potential explanations for this heterogeneity.

This Statistical Analysis Plan (SAP) provides an in-depth description of the statistical methods and definitions for the study analysis. More information on the rationale and data sources can be found in the Study Protocol.

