Assumption 2. We will explicitly incorporate co-occurring interventions in a seven-day period as a combination of interventions. We will also adjust for changes in the case definition of COVID-19 cases and deaths for each of the respective outcomes. We will report in the Supplementary Appendix the exact dates considered in the analysis for each country/subnational unit and the interventions included in each intervention period.

Assumption 3. We will introduce flexible spline functions to account for seasonality and long-term trends. We will add a scale parameter, which will be the Pearson statistic divided by the residual degrees of freedom, to account for potential overdispersion (a violation of the Poisson regression assumption). We will test for autocorrelation using the Durbin-Watson tests and visual plots of the autocorrelation function and partial autocorrelation function. If there is evidence of autocorrelation, we will use the Newey-West method to obtain adjusted standard errors.

Therefore, in the final analysis, we will use Poisson regression to model the count data.. The final model is an extension of the regression described in equation 1 with the specifications described above. The model will include each of the interventions (either as single interventions or combinations of), denoted  $j = 1, \dots, J$ . This method allows estimating simultaneously the effect of several interventions. We will consider interventions implemented within a 7-day period as a combination of interventions, following previous studies. This means that the maximum number of combinations of interventions is 52,  $t = 1, \dots, 52$ . We will estimate the effect of the interventions separately when interventions are separated by at least seven consecutive days and for a maximum period of 30 days. The primary analysis will include a 7-day lag to account for the delay in the intervention to be effective, considering the incubation period of SARS-COV2.

$$(5) \ln(Y_t) = \beta_0 + \beta_{1j}time_{tj} + \beta_{2j}post_{tj} + \beta_{3j}timepost_{tj} + \mu_t$$

This model will be run at the municipal level and, therefore, we expect to run 10,000 regressions multiplied by the number of combinations of interventions at each municipal level. Coefficient  $\beta_{3j}$  is the coefficient of interest and represents the change in slope after the intervention  $j$  at period  $t$ .

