In coefficient of interest at a second stage, we will pool the effects for each intervention -or combination of interventions- (i.e. the coefficient of interest  $\beta_{3j}$  from the local level regression) using a random-effects meta-analysis. This meta-analysis will provide information to obtain a pooled effect estimate and a measure of heterogeneity. We will use the  $I^2$  as a measure of heterogeneity.

If the heterogeneity is moderate or high ( $I^2$  higher than 50%), we will carry out a meta-regression to assess whether subnational level determinants can explain the observed heterogeneity. We will analyse the following covariates: (i) Population size, (ii) Population density, (iii) Proportion of population over 60 years old, as a proxy for age structure of the population, (iv) Household density, and (iv) Proportion of population with basic education, as a proxy of socioeconomic status.

The meta-regression has the effect size  $\widehat{\theta}_k$  of a first-stage regression  $k$  as the outcome, covariates  $x_{ik}$ , a fixed effect  $\rho_1 S_a$  for the second-tier level  $a$  (i.e. State or Region) and a random-effect  $\delta_2 N_b$  for the national level  $b$  and a fixed effect  $\rho_2 Y$  for the time of the year (quarterly periods)(equation 6). The equation includes two types of independent errors, where  $\varepsilon_k$  is the sampling error of the effect size and  $\varsigma_k$  is the random-effect error term.

$$(6) \theta_k = \gamma_1 x_{1k} + \dots + \gamma_n x_{nk} + \rho_1 S_a + \delta_2 N_b + \rho_2 Y + \varepsilon_k + \varsigma_k$$

These controls for higher levels of administration and time of the year will allow us to control for constant characteristics at the subnational and national level, as well as changes in the effectiveness throughout the pandemic.

We will carry out the following sensitivity analyses: (1) comparison of effect estimates using a 5-day and 10-day lag; (2) quasi-myopic analyses to control for anticipatory effects (if there is evidence of), and (3) placebo tests evaluating changes at times when no policy was implemented. In the analyses for the number of cases and time-varying R, we will run additional sensitivity analyses estimating the number of SARS-CoV-2 cases corrected by under-ascertainment derived from mortality statistics.

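### The I² planned for each intervention mixes country, state and municipal variation, so it cannot by itself answer the aim on local heterogeneity

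*SAP*

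**What the plan says.** The SAP (Introduction) gives the second aim as: "second, to examine the effect heterogeneity of transmission and mortality at the local level". The Protocol's opening section gives the reason for it: "Inequalities in policy effectiveness can arise due to within-country differences at the local level".

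The first stage fits a separate interrupted time series in each municipality. The SAP (Analysis methods) puts the scale at: "we expect to run 10,000 regressions multiplied by the number of combinations of interventions at each municipal level". The municipalities lie in nine countries (Protocol, Design and setting): "To date, eligible countries are Argentina, Brazil, Chile, Colombia, Costa Rica, Guatemala, Mexico, Paraguay, and Peru".

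At the second stage the SAP states: "we will pool the effects for each intervention -or combination of interventions". It describes no state or country level there, names I² as the measure, and adds: "This meta-analysis will provide information to obtain a pooled effect estimate and a measure of heterogeneity". The Protocol (Statistical analysis) says this step will show "the degree of heterogeneity between the effects at the local level", and then: "If we observe high levels of heterogeneity (defined as higher than 50%), we will also use standard meta-regression techniques".

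State and country appear only in the meta-regression, equation 6 of the SAP. It has a state fixed effect, a country random effect, a quarter effect, the local covariates, a sampling error and a residual random-effect term. The SAP presents the state, country and quarter terms as controls. The Protocol (Covariates) also plans to look at how heterogeneity changes after covariate adjustment, without naming a statistic or a level.

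**The concern.** A random-effects meta-analysis with a single level treats the municipal estimates as one exchangeable set. Its I² is the share of total variation that is not sampling error, whatever the source. If a policy worked differently in different countries but alike in every municipality of a country, I² could be large. So could it be if every country were alike and municipalities differed. For an aim motivated by differences within countries these are opposite findings, and the planned statistic can take the same value in both.

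Two things are at stake: what the study reports as its answer to the second aim, and the rule that starts the search for local explanations, since both rest on this I². The point is about what the heterogeneity figure measures. It does not concern the standard error of the pooled effect.

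**Working it through.** **No figure to reproduce.** The documents give no expected I², between-unit variance or standard error for this step. All variances below are assumptions, expressed relative to the typical sampling variance of a municipal estimate, which is set to 1.

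**Formula.** I² = max(0, (Q − df)/Q). Approximately:

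I² ≈ (V_country + V_state + V_municipality) / (V_country + V_state + V_municipality + 1)

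Only the sum of the three variances enters.

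**Between-state variance only, no municipal variance.**
- 0.5: 0.5/1.5 = 33%
- 1: 1/2 = 50%
- 2: 2/3 = 67%

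**Municipal variance only, 2:** 2/3 = 67%, the same as the line above it.

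**Simulation.** From the documents: nine countries and about 10,000 municipalities. Assumed: 100, 200 or 300 states, and equal or lognormal sampling variances, with 60 runs per setting. The within-country and within-state I² use Q around country and state means. Ranges run over the six combinations of state number and variance pattern.

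| Variance: country / state / municipality | Total I² | Within-country I² | Within-state I² | Runs with total I² > 50% |
|---|---|---|---|---|
| 0 / 0 / 0 | 0.3–0.7% | 0.3–0.6% | 0.4–0.7% | 0% |
| 0 / 0.5 / 0 | 32.7–33.5% | 30.9–32.7% | 0.4–0.6% | 0% |
| 0 / 1 / 0 | 49.4–50.0% | 47.4–49.4% | 0.6–0.7% | 38–50% |
| 0 / 2 / 0 | 66.1–66.8% | 64.5–66.2% | 0.6–0.7% | 100% |
| 1 / 1 / 0 | 63.1–65.0% | 47.5–49.2% | 0.4–0.8% | 100% |
| 2 / 0 / 0 | 58.2–62.0% | 0.4–0.7% | 0.4–0.7% | 72–88% |
| 0 / 0 / 2 | 66.7–66.8% | 66.6–66.8% | 65.7–66.8% | 100% |
| 0 / 0.25 / 0.5 | 42.5–42.8% | 41.9–42.6% | 32.2–33.4% | 0% |

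The row 2 / 0 / 0 is the clearest case. Total I² is about 60% with no variation at all inside any country. The last row is the reverse: real municipal variation, but total I² below 50%, so equation 6 is not run and nothing by level would be reported.

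**Illustration on the scale of the slope change.** Assume independent daily Poisson counts with a flat mean m, 30 days before and 30 after, and no overdispersion. The slope change is the difference of two slopes, each with variance 12/(m·30·(30² − 1)), so:

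SE = √(24/(m·30·899)) = 0.0298/√m

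This gives 0.0298, 0.0133 and 0.0067 per day at 1, 5 and 20 cases a day. Take an SD of 0.02 per day lying wholly above the municipality (also assumed):
- 1 case a day: 0.0004/(0.0004 + 0.00089) = 31%
- 5 cases a day: 0.0004/(0.0004 + 0.00018) = 69%
- 20 cases a day: 0.0004/(0.0004 + 0.000044) = 90%

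With overdispersion of 3 these become 13%, 43% and 75%. The planned outcome is a rounded 7-day average, so actual standard errors will differ. Whether total I² passes 50% thus depends strongly on case counts, which say nothing about where the heterogeneity lies.

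**The case against.** The strongest reply is equation 6. A reader might infer that nothing in the plan isolates the local part, and the SAP does not support that. With state fixed effects in the model, the residual random-effect term is close to a within-state, between-municipality component, and the covariate coefficients rest on variation within states. If municipalities of the same state did not differ, the true coefficients would be zero and the residual variance near zero. I² above 50% is also exactly the condition under which equation 6 is run. A false local explanation therefore does not simply follow from a high I².

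That reply stands as far as it goes. It leaves three gaps. Equation 6 is run only above 50%, so an intervention below the limit gets no measure by level. Its residual is adjusted for covariates and quarter, and the plan does not designate it as the result for the second aim. Because states nest in countries, the state fixed effects absorb both country differences and differences between states of one country, so the model cannot give a within-country total or a country share.

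A second reply is that local level may simply mean among local-government estimates. On that reading total I² does describe the spread. The Protocol's stated motive of within-country differences favours the narrower reading, but the aim itself is not explicit.

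Three further inferences go too far. I² need not be high, since the table shows 33% in a case with no municipal variance. There is not a single I² for the study: there is one for each intervention or combination and outcome, and a given intervention need not occur in all nine countries. Nor do the documents limit the second aim to differences within states, because within-country differences include those between states.

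**Conclusion.** The point holds as a mismatch between the second aim and its designated statistic. For each intervention, the planned I² cannot distinguish variation above the municipality from variation between municipalities: a variance of twice the sampling variance gives about 67% whether it lies between states or between municipalities. With no difference between municipalities of the same state, I² tends to exceed 50% once the higher-level variance exceeds the typical sampling variance. At equality it does so in 38–50% of runs, and at half that variance in none.

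These sizes rest on assumed variance ratios and state counts. The conclusion that only the sum of the variances enters I² does not depend on them. The importance of the point does depend on reading the second aim as within-country heterogeneity, which the Protocol's opening section supports.

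A reader might infer that the second aim will be answered wrongly. The documents do not show that: it depends on unknown variances and on how equation 6 is reported. What they show is that the planned I² could mislead and that no reported result is assigned to correct it. The change should be made before analysis.

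**What to change.** For each intervention or combination and each outcome:

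1. Fit a multilevel random-effects meta-analysis with municipality within state within country, whether or not total I² exceeds 50%.
2. Report tau² with an interval, and its share of the heterogeneity, at country, state and municipal level. Total I² can stay as a description.
3. State in the SAP that the second aim is answered from the within-country components, with state and municipality shown separately.
4. Base the step to local explanations on those components, and write the rule down. If a 50% limit is kept, say which I² it applies to. Where the state component dominates, note that the state fixed effects in equation 6 absorb it, so the local covariates there cannot explain it.

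The cost is SAP wording and a standard model on the same first-stage estimates, with the routine named under Statistical software. No new data are needed. The country variance rests on at most nine countries, and on fewer where an intervention was not used everywhere, so its interval will be wide. The municipal component is better supported, with about 10,000 municipalities overall, though fewer for any one intervention. An intervention seen in one country only, or in few municipalities per state, will not support all three levels. The SAP should say which level is dropped in that case.

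### With no minimum event count, sparse rounded counts can give the meta-regression a false population-size gradient and bias the pooled slope change

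*SAP*

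**What the plan says.** All quotes are from the SAP, Analysis methods.

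- **First stage.** In the final analysis "we will use Poisson regression to model the count data", one municipality at a time: "This model will be run at the municipal level and, therefore, we expect to run 10,000 regressions", multiplied by the number of intervention combinations. The coefficient carried forward "represents the change in slope after the intervention".
- **Outcome.** Under Outcome definitions, cases and deaths enter as seven-day averages rounded to whole numbers. The time-varying reproduction number is a separate outcome.
- **Standard errors.** "We will add a scale parameter, which will be the Pearson statistic divided by the residual degrees of freedom". If autocorrelation is found, "we will use the Newey-West method to obtain adjusted standard errors".
- **Second stage.** The slope changes are pooled by random-effects meta-analysis. If I² exceeds 50%, they go into the meta-regression of equation 6: "We will analyse the following covariates: (i) Population size, (ii) Population density", then age structure, household density and education. Of its error terms, sampling and random-effect, the SAP says "The equation includes two types of independent errors".
- **Who is included.** Under Sample size, all available data that meet the inclusion criteria are used. There is no minimum event count and no rule for series that are mostly zero.
- **Sensitivity analyses.** These are other lags, exclusion of anticipation periods, placebo dates and correction for under-ascertainment. None restricts by event count, and the placebo dates are not said to be carried into the meta-regression.

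**The concern.** Many third-tier units will have few cases, and fewer deaths, in the weeks around a policy. Two things then go wrong, both depending on the size of the place.

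First, a small average rounded to a whole number becomes a run of zeros and ones, and the slope fitted to that run is biased. Second, the standard error of a Poisson slope depends on the fitted counts. A place where counts fall after the policy gets a larger standard error, and so less weight, than one where they rise.

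Both effects fade as counts grow, so both vary with population size, the first covariate tested. At stake are the third aim, explaining local heterogeneity, and the pooled effect under the first aim.

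**Working it through.** **No figure to reproduce.** The documents give no event counts, effect size, second-stage weights or coding for population size. What follows shows what the planned steps do under stated assumptions.

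**Assumptions.** 4,000 municipalities; 30 days before and 30 after the policy (the SAP's 30-day maximum for the latter); growth of 0.05 per day; events in the 30 pre-policy days lognormal with median 7 or 20 and SD of log 1.3; true slope change with mean 0 or −0.05 per day and SD 0.03, unrelated to size; weights 1/(SE² + τ²); meta-regression on log size. On the rounded outcome, the Pearson scale was applied and units with fewer than 2 non-zero days on either side were dropped. Each scenario had 20 to 40 replicates.

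**What rounding does.** A seven-day total of 3 gives 3/7 = 0.43, which rounds to 0. A total of 4 gives 0.57, which rounds to 1. With growth of 0.05 per day over 30 days:

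- Share of events in the last pre-policy week: (1 − e^−0.35)/(1 − e^−1.5) = 0.295/0.777 = 0.380.
- Share in the first week: 0.380 × e^−1.15 = 0.120.
- With 20 events, the first week averages 20 × 0.120/7 = 0.34, which rounds to 0. The last week averages 20 × 0.380/7 = 1.09, which rounds to 1.

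Smooth growth becomes a jump from 0 to 1. The pre-policy slope is overstated and the slope change is pushed downward, towards benefit. With 40 events the first week averages 40 × 0.120/7 = 0.69, which rounds to 1, and the distortion is much smaller.

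**Simulation, no true gradient, all municipalities.**

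| | Rounded 7-day average (as planned) | Unrounded daily counts |
|---|---|---|
| False gradient per tenfold size | about +0.05 to +0.10 | about −0.003 to −0.005 |
| Runs with p < 0.05 | 100% | 45% to 85% |
| Bias of pooled slope change, per day | about −0.014 to −0.037 | about +0.001 to +0.003 |
| Mean I² | about 0.95 | 0.40–0.46 (median 7), 0.65–0.69 (median 20) |

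Against an effect of −0.05, the rounded gradient is 0.05/0.05 = 100% to 0.10/0.05 = 200% of the effect per tenfold size. The unrounded one is 6% to 10%. The pooled bias on the rounded outcome is 0.014/0.05 = 28% to 0.037/0.05 = 74%.

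**Which cause dominates.** A separate simulation used 1,500 units, effect −0.05, SD 0.03 and incidence of 5, 20 or 100 per 100,000 per day.

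| Outcome modelled | Gradient per tenfold population (5 / 20 / 100) |
|---|---|
| Rounded 7-day average | +0.065 / +0.024 / +0.005 |
| Same average, not rounded | +0.004 / +0.001 / +0.000 |
| Raw daily counts | −0.0026 / −0.0017 / −0.0009 |
| Rounded, weights freed of dependence on the slope | +0.195 / +0.082 / +0.012 |

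Without rounding, most of the gradient disappears. Freeing the weights from the slope makes it larger. Rounding is therefore the main cause for the planned outcome, and the correlation between estimate and standard error works against it.

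**Minimum of 40 pre-policy events, rounded outcome.** The residual gradient was at most +0.0043, with false significance in 0% to 15% of runs. A pooled bias of about +0.002 per day remained when the true effect was −0.05. The share of all municipalities above 40 events is 1 − Φ(ln(40/7)/1.3) = 1 − Φ(1.34) = 9% at median 7, and 1 − Φ(ln(40/20)/1.3) = 1 − Φ(0.53) = 30% at median 20. Counted against only those whose rounded series can be fitted, it reaches about 40%.

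**The case against.** **The independence sentence is standard.** It concerns the two error terms of a meta-regression, not the relation between an estimate and its standard error. A reader might infer that this sentence is the mistake. It is not: the correlation between estimate and weight exists even when τ = 0, and rewording the sentence would change nothing.

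**The direction may be misjudged.** From the weighting argument alone, a reader might infer that policies will seem to work less well in small places and that the pooled effect will be pulled towards no benefit. That holds only for unrounded daily counts, where the gradient is small. At median 7 the I² condition would also usually not be met there, so the meta-regression would not be run. For the outcome the SAP defines, both directions reverse.

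**The plan has some protection.** The Pearson scale and Newey–West methods change standard errors, not biased slopes. In the 1,500-unit simulation on the rounded outcome, Newey–West errors still gave false significance in 100%, 100% and 35% of runs at the three incidences. Placebo dates could expose a false gradient, but only if carried through equation 6.

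**The inputs are assumed.** This stands. The documents give neither event counts nor the number of municipalities per intervention combination. At a median of 100 events the rounded gradient fell to +0.012, though it was still significant in every run. The splines, the state and quarter fixed effects, the country random effect and the other covariates were not simulated.

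**A threshold discards data and truncates the covariate under test.** This also stands, and is why the full fit should be shown beside the restricted one.

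**Conclusion.** The concern holds in this form: with no minimum count, the planned second stage can report a size gradient, and a pooled bias, that do not exist. For the rounded case and death outcomes the main cause is rounding of small averages, and the error favours small places. The I² condition gives no protection there: I² was about 0.95, and 0.89 in the 1,500-unit simulation even with no true heterogeneity (incidence 20 per 100,000 per day).

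The sizes rest on the assumed medians of 7 to 20 pre-policy events, 4,000 units and effect SD 0.03. The documents do not support saying that a false gradient is certain, nor any particular magnitude for the real data. The time-varying reproduction number is not a count and is outside this point. The change should be made before analysis. Confidence is medium because the event counts are unknown.

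**What to change.** In the second-stage text of the SAP's Analysis methods, for cases and deaths only:

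1. Pre-specify that equation 6 and the pooled effect are also fitted on municipalities above a minimum number of pre-policy events in the model window, shown beside the all-municipality fit. Forty is an example, to be confirmed by simulation on the rounded outcome.
2. Claim a size or density gradient only if it holds in the restricted set.

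**Cost.** SAP wording and one extra run per count outcome. Under these assumptions the restricted set keeps about 10% to 40% of municipalities. The standard error of the gradient was about 2 to 4 times larger in the daily-count simulations. Conclusions, above all for deaths, would cover mostly larger places. A pooled bias of about +0.002 per day (0.002/0.05 = 4% of an effect of −0.05) would remain. At a median of 100 events the restricted fit still gave false significance in 15% to 20% of runs, with a gradient under 0.001, so the size of any gradient should be reported with its p-value.
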